**Table 3. Treatment Summary**

LTE Lead-in Study	Lead-in Study Assigned Treatment	Dose Q4W for 24 weeks a
RD.06.SPR.202699	Nemolizumab 30 mg (1 injection)	Blinded Nemolizumab 30 mg (1 injection)
	Nemolizumab 2 × 30 mg (2 injections)	Blinded Placebo (1 injection)
		Blinded Nemolizumab 2 × 30 mg (2 injections)
		Blinded 2 × Placebo (2 injections)

Abbreviation: LTE = long-term extension; Q4W = every 4 weeks.

aDose will be assigned based on dose received in LTE lead-in study.

Clinical assessments will occur according to the Schedule of Assessments in the protocol through the Week 24 visit.

If a subject meets the criteria for relapse at any point, the subject will exit the study and re-enter the LTE study (see [Figure 2](#)). Subjects who exit the study before Week 24 should complete an early termination (ET) visit. Subjects who complete the study through Week 24 are eligible to re-enroll in the LTE study.

Subjects who prematurely discontinue study drug for reasons other than relapse will be encouraged to complete the scheduled study visits. These subjects will only be eligible for re-enrollment in the LTE study if they continue with study visits through Week 24.

Subjects who discontinue the study for reasons other than relapse before Week 24 or who will not continue nemolizumab treatment in the LTE study should complete a follow-up visit, 12 weeks ( $\pm 7$  days) after the last study drug injection.

[figure not shown]

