4.1. Brief Description

This is a Phase 3b multicenter, randomized, double-blind, placebo-controlled, parallel-group study to evaluate the durability of response and safety of nemolizumab in adult subjects who participated in the nemolizumab PN LTE study (RD.06.SPR.202699) and achieved a clinical response (i.e., IGA score of 0 or 1 and ≥ 4 -point improvement in weekly average of PP NRS score from baseline of the lead-in study) at Week 52 of the LTE study.

[figure not shown]
Subjects who agree to enroll in this study must do so at the time of completion of the Week 52 visit in the LTE study (RD.06.SPR.202699) to prevent any lapse in study treatment. After the Week 52 visit of the LTE study is complete, approximately 100 subjects who choose to enter this study will be randomized 1:1 to receive either 1 or 2 injections of nemolizumab or placebo, stratified by dosing regimen. Subjects will continue to receive the same dosing regimen received in the LTE study (i.e., 1 or 2 SC injections of study drug administered every 4 weeks [Q4W]). Subjects with a body weight <90 kg in LTE study will receive a 30-mg dose. Subjects weighing ≥ 90 kg in the LTE study will receive a 60-mg dose.

Subjects' participation in the study will be up to approximately 32 weeks. The study consists of a 24-week treatment period and an 8-week follow-up period (12 weeks after their last study drug injection at Week 20).

Relapse is defined as an increase in (weekly average of the) PP NRS score ≥ 4 points from baseline or an increase in IGA score ≥ 2 from baseline at any point during the study. If a subject meets the criteria for relapse, then the subject may be considered for re-entry into the LTE study (RD.06.SPR.202699). Refer to [Figure 4-1](#) for subject transition between studies 202699 and 203890.

This document is confidential.

Figure 4-1: Subject Transition between Studies 202699 and 203890

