4.6. Study Procedures and Flowchart

See [Table 4-1](#) for study procedures.

This document is confidential.

Table 4-1: Schedule of Assessments

	Baseline ^a	Treatment Period						FU	ET	Unscheduled
Visit	V1	V2	V3	V4	V5	V6	V7	V8		
Week	W0 (Day 1)	W4	W8	W12	W16	W20	W24	W32	if applicable ^b	if applicable ^c
Visit Window (days)		±1	±3	±3	±3	±5	±5	±7		
ICF ^a	X									
Inclusion/exclusion	X									
Demographics	X									
Medical history, previous therapies and procedures, smoking status	X									
Patient-Reported Outcomes										
PP NRS/ SD NRS ^{d, e}	X							X	(X)	
DLQI ^e	X				X		X	X	(X)	
Efficacy Assessments										
IGA	X	X	X	X	X	X	X	X	(X)	
Safety Assessments										
ACT ^{e, f}	X	X	X	X	X	X	X	X	(X)	
Respiratory examination	X	X ^g	X ^g	X	X ^g	X ^g	X	X	(X)	
PEF testing	X	X ^g	X ^g	X	X ^g	X ^g	X	X	(X)	
Vital signs ^h	X	X	X	X	X	X	X	X	(X)	
Full physical examination	X			X			X	X	(X)	
Symptom-directed physical examination		X	X		X	X				
Height	X								(X)	
Weight	X					X		X	(X)	
12-lead ECG ⁱ	X					X		X	(X)	
Contraceptive counseling	X								(X)	
Adverse events ^e	X	X	X	X	X	X	X	X	(X)	
Concomitant therapies and procedures ^e	X	X	X	X	X	X	X	X	(X)	
Laboratory Assessments										
Blood samples for hematology and clinical chemistry ^j	X			X			X	X		(X)
Urinalysis	X			X			X	X		(X)
Urine pregnancy test ^k	X	X	X	X	X	X	X	X	(X)	

This document is confidential.

	Baseline ^a	Treatment Period							FU	ET	Unscheduled
Visit	V1	V2	V3	V4	V5	V6	V7	V8			
Week	W0 (Day 1)	W4	W8	W12	W16	W20	W24	W32		if applicable ^b	if applicable ^c
Visit Window (days)		±1	±3	±3	±3	±5	±5	±7			
FSH ⁱ	X									(X)	
Blood sample for virology (HIV, Hepatitis B and C)										(X)	
Blood sample for TB test										(X)	
POE & Immunogenicity Assessments											
Blood sample for POE ^{c, m}	X							X		X	(X)
Blood sample for ADA ^{c, m}	X							X		X	(X)
Study Drug Administration											
Randomization	X										
Study drug injection ^{n, o, p, q, r}	X	X	X	X	X	X				(X)	

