8.4. Visit Windows

Efficacy by-visit summaries will use the analysis visit. All visits including unscheduled and early termination visits will be windowed based on the analysis visit window in [Table 8-1](#) which is based on study day. If multiple measurements are taken within the same window, the one taken closest to the target study day will be used for the analysis. If there are multiple measurements with same difference from target day, the later assessment should be used for the analysis.

Table 8-1: Analysis Visit Window

Analysis Visit	Target Study Day	Visit Window (IGA)	Visit Window (DLQI)
Baseline	1	≤ 1	≤ 1
Week 4	29	2 to 42	N/A
Week 8	57	43 to 70	N/A
Week 12	85	71 to 98	N/A
Week 16	113	99 to 126	2 to 140
Week 20	141	127 to 154	N/A
Week 24	169	155 to 210	141 to 210
Week 32 Follow-up	225	>211	N/A

All daily diary efficacy data will be classified into analysis visits as described in [Table 8-2](#) considering the data during the 7 days immediately preceding the target day of analysis visit.

Analysis visit of diary (ePRO) data will be defined depending on the data collection as below.

Consecutive daily assessment:

For the evening assessments (PP NRS), the daily data collected up to Week 24 will be classified into analysis visits considering the data during the 7 days immediately preceding the target study day of analysis visit. Similarly, for the morning assessment (SD NRS, morning sleep diary), the 7 days data up to the target study day will be classified into analysis visit. Details of the analysis visit window are in [Table 8-2](#) below.

This document is confidential.

Table 8-2: Analysis Visit Window for Evening and Morning Assessments

Analysis Visit	Target Study Day of Analysis Visit	Visit Window for evening assessment (PP NRS, AP NRS)	Visit Window for morning assessment (SD NRS, morning sleep diary)
Baseline	1	-7 to -1	-6 to 1
Week 1	8	1 to 7	2 to 8
Week 2	15	8 to 14	9 to 15
Week 3	22	15 to 21	16 to 22
Week 4	29	22 to 28	23 to 29
Week 5	36	29 to 35	30 to 36
Week 6	43	36 to 42	37 to 43
Week 7	50	43 to 49	44 to 50
Week 8	57	50 to 56	51 to 57
Week 9	64	57 to 63	58 to 64
Week 10	71	64 to 70	65 to 71
Week 11	78	71 to 77	72 to 78
Week 12	85	78 to 84	79 to 85
Week 13	92	85 to 91	86 to 92
Week 14	99	92 to 98	93 to 99
Week 15	106	99 to 105	100 to 106
Week 16	113	106 to 112	107 to 113
Week 17	120	113 to 119	114 to 120
Week 18	127	120 to 126	121 to 127
Week 19	134	127 to 133	128 to 134
Week 20	141	134 to 140	135 to 141

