10.1. Primary Efficacy Endpoints

10.1.1. Primary Analysis of Primary Efficacy Endpoint

The primary endpoint is the time to relapse which is defined as meeting at least 1 of the following criteria:

- Increase in (weekly average of the) PP NRS score ≥ 4 points from baseline
- Increase in IGA score ≥ 2 points from baseline;

For primary endpoint, any subjects with missing data for PP NRS and IGA Score both at visit will be censored at the respective timepoint. If any one of PP NRS or IGA Score data is available for the visit, calculation for primary endpoint will be made using available results. If a subject has taken prohibited medication at any point of time during treatment period, then subject will be censored at the respective visit.

The primary endpoint will be analyzed using Cox proportional hazard model with treatment group, dosing regimen as a factor, and baseline PP NRS score and IGA score as covariates on ITT population. The estimated hazard ratio and the corresponding 95% CI will be presented. A supportive analysis also will be performed using Per-Protocol Population.

Kaplan-Meier survival plots will also be presented for time to relapse. The median time, 25th and 75th quantiles along with corresponding CI will be presented using ITT/PP.

Censoring rule for primary endpoint variable is as follows:

Situation	Date of Progression or Censoring	Outcome
Relapse as described	Date of Relapse	Event
Subject withdrawn without relapse	Date of last efficacy assessment (PP NRS and IGA) prior to withdrawal	Censored
Treatment Discontinuation	Date of last efficacy assessment (PP NRS and IGA) prior to Treatment Discontinuation	Censored
Prohibited medication without relapse	Date of last efficacy assessment (PP NRS and IGA) prior to prohibited medication	Censored
Completes the study without relapse	Date of Week 24 completion	Censored
No Efficacy assessment	Date of study Day 1	Censored

This document is confidential.

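### The closest-to-target window rule in SAP 8.4 can drop an IGA relapse seen at an early termination visit from the two by-visit IGA endpoints

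*SAP*

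**What the plan says.** SAP 8.4 sets its scope first: "Efficacy by-visit summaries will use the analysis visit". It then pools visit types: "All visits including unscheduled and early termination visits will be windowed based on the analysis visit window" in Table 8-1. Within a window, "If multiple measurements are taken within the same window, the one taken closest to the target study day will be used for the analysis", and for ties, "If there are multiple measurements with same difference from target day, the later assessment should be used for the analysis". Neither a relapse value nor the last reading before exit is exempted. For diary scores, Table 8-2 has a separate early termination row; Table 8-1 has none for IGA.

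Relapse includes an "increase in IGA score ≥ 2 from baseline at any point during the study" (SAP 4.1). Its consequence is in Protocol 7.1, under Table 3: "If a subject meets the criteria for relapse at any point, the subject will exit the study and re-enter the LTE study". Subjects who relapse should complete an ET visit (footnote b of the Schedule of Assessments), and IGA is collected there (SAP 10.2.1).

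Both IGA endpoints are analysed on observed cases (OC) and again with missing values counted as failure or relapse (SAP 10.2 and 10.2.1). SAP 10.1.1 handles the primary endpoint separately: its censoring table makes a relapse an event on the date of relapse.

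**The concern.** A subject who relapses leaves the study, so the ET reading is often the last IGA and may be the only one that shows the relapse. If the subject attended a scheduled visit a few days earlier, both readings can share a window, and the rule may keep the earlier, favourable one. No later IGA exists to correct the record.

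Baseline IGA is 0 or 1 by inclusion criterion 1, so a rise of at least 2 points always takes the subject out of IGA success. One dropped reading therefore affects both endpoints. A withdrawal study expects more relapses on placebo. If that happens, the loss falls mainly on that arm, pulls the by-visit IGA comparisons towards no difference, and makes IGA response after withdrawal look better kept than it was.

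**Working it through.** The plan states no figure to reproduce, so the check applies Table 8-1 and the selection rule day by day.

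**Inputs.** Targets and IGA windows come from SAP Table 8-1. Permitted visit deviations come from SAP Table 4-1: "Visit Window (days) ±1 ±3 ±3 ±3 ±5 ±5 ±7" for Weeks 4, 8, 12, 16, 20, 24 and 32.

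**Formula.** Each window from Week 4 to Week 20 ends 13 days after its target. Let k be the number of days between the scheduled visit and its target.
- Visit on target or late: every later reading in the window is further from target, so days target + k + 1 to target + 13 are dropped.
- Visit early: a later reading up to target + k is nearer or tied and replaces it (the tie goes to the later reading). Days target + k + 1 to target + 13 are dropped.

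Either way, days exposed = 13 − k.

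| Window | Target | Range | Permitted deviation | Exposed, visit on target | Exposed, visit at limit |
|---|---|---|---|---|---|
| Week 4 | 29 | 2–42 | ±1 | 13 | 12 |
| Week 8 | 57 | 43–70 | ±3 | 13 | 10 |
| Week 12 | 85 | 71–98 | ±3 | 13 | 10 |
| Week 16 | 113 | 99–126 | ±3 | 13 | 10 |
| Week 20 | 141 | 127–154 | ±5 | 13 | 8 |
| Total | | | | 65 | 50 |

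**Example.** Baseline IGA 1; Week 8 visit on Day 57, IGA 1; ET on Day 66, IGA 3. Both fall in 43–70. The distances from target are 0 and 9, so Day 57 is kept and the relapse is dropped. An ET reading on Day 71 would go to Week 12 and be kept. With the Week 8 visit on Day 54, ET readings on Days 55–60 would win and only Days 61–70 would be lost.

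**What happens to that subject in the by-visit analyses.**

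| Analysis | Week 8 | Later visits |
|---|---|---|
| OC | success, no increase | absent |
| Missing as failure or relapse | success, no increase | failure or relapse at each later listed visit |

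The SAP 10.2 table lists IGA success to Week 24 but the IGA increase only to Week 16, although SAP 5.2 defines the latter at each scheduled visit. As listed, an IGA increase dropped from the Week 16 window (Days 114–126 for an on-target visit) is not recovered even by imputation.

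**Weight of one subject.** SAP 4.3 expects about 40 randomized, hence 20 per arm at 1:1. One misclassified subject moves that arm's proportion in that window by 1/20 = 5 percentage points, and by more under OC once others have left. With the roughly 100 subjects given in SAP 4.1, it would be 1/50 = 2 points.

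**The case against.** A reader might infer that the primary analysis loses these relapses too, because SAP 10.1.1 says: "If any one of PP NRS or IGA Score data is available for the visit, calculation for primary endpoint will be made using available results". The documents do not support this. SAP 8.4 is limited to by-visit summaries, and time to relapse is not one. SAP 10.1.1 dates the event and the censoring times by calendar date, and relapse counts at any point. The quoted sentence deals with one of the two measures being missing, not with choosing between two IGA readings. A subject with a relapse-level IGA at ET meets the event definition. What remains is a gap in wording: nothing says outright that readings not selected under 8.4 still count.

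A reader might also infer that about half of between-visit relapses are lost. With on-target visits, 65 of the 135 between-visit days from Day 30 to Day 168 are exposed (48%). Adding Days 2–28, where nothing is lost, gives 65/162 = 40%. These are shares of days, not of relapses. To read them as shares of relapses assumes evenly spread ET timing, and the documents give neither relapse rates nor ET timing. A relapse seen at a scheduled visit is not lost by this route.

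Two further points against the concern stand. OC loses every subject after exit whatever the window rule, so only the score in the exit window is due to this rule. And closest-to-target selection does not depend on the outcome. A remedy that gave precedence only to relapse readings would depend on it.

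**Conclusion.** The defect is real but confined to two secondary endpoints: maintained IGA success, and IGA increase of at least 2 points, by visit. In each window from Week 4 to Week 20, an ET or unscheduled relapse reading on 8 to 13 days after the scheduled visit can be discarded. That range assumes scheduled visits within their permitted windows; 13 applies only to a visit exactly on target. The subject counts as not relapsed in that window and, under OC, never shows the IGA relapse. Imputation recovers the subject at later listed visits only, and for the IGA increase none is listed after Week 16.

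The direction, towards no difference, rests on placebo subjects relapsing more. The number affected cannot be computed, and it is zero if no IGA relapse is found between visits. Loss from the primary endpoint is not shown; SAP 10.1.1 needs a clarifying sentence, not a correction.

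**What to change.** 1. **SAP 8.4.** When the scheduled visit for a window has been attended, assign any later ET IGA, whatever its value, to the next scheduled analysis visit. Treat an unscheduled IGA that is the subject's last reading before exit in the same way. An alternative is to use the last reading in the window for subjects who exit.
2. **SAP 10.2 table.** Reconcile the visits listed for the IGA increase with SAP 5.2. Otherwise a reading carried from the Week 16 window to Week 20 has no listed visit.
3. **SAP 10.1.1.** State that time to relapse uses every post-baseline IGA and weekly PP NRS, including ET and unscheduled visits, before any window selection.

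The cost is a few sentences, one corrected table row and a small change to the record-selection flag. The downside of the first option is distance from the nominal day: after an on-target visit, a carried reading lies 28 − 13 = 15 to 28 − 1 = 27 days before its new target, and somewhat further if the scheduled visit was early. The alternative keeps the reading within 13 days of its target but displaces the scheduled reading.

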### 5.3 Risk/Benefit Assessment

Pruritus is the cardinal symptom in PN and is often difficult to treat with current therapies. Chronic itching is believed to induce and maintain the characteristic PN skin lesions through an itch-scratch cycle. Therefore, the goal of PN treatments target pruritus remission to allow skin healing and improvement in patients' QoL.

Results of a previous clinical study with nemolizumab demonstrated a marked effect on both PN lesions and pruritus. The decrease in itching sensation was rapid, within the first week following the first injection and improved with subsequent administrations. This improvement in the signs and symptoms of PN was consistent with the observed improvement in QoL (evaluated using the Dermatology Life Quality Index [DLQI]). Continuous treatment with nemolizumab also led to an improvement in the overall severity of PN, which was evaluated with various scales (i.e., Investigator Global Assessment [IGA], Peak Pruritus [PP] Numeric Rating Scale [NRS], and Prurigo Activity Score). Based on the results of the Phase 2a study (RD.03.SPR.115828) nemolizumab was clinically and statistically significantly superior to placebo in reducing the weekly average of PP NRS scores at Week 4 (difference between treatment groups -38.0%; 95% confidence interval [CI] -51.0, -25.0;  $p<0.001$ ). The statistically significant improvements in IGA success and Prurigo Activity Score observed in the nemolizumab group were greater than those observed in the placebo group.

Based on the currently available information on nemolizumab and the risks associated with biologic agents in general, the important potential risks of nemolizumab treatment include local and systemic injection-related reactions, newly-diagnosed asthma or worsening of asthma, exacerbation of AD, and skin and non-skin infections.

The following specific risk-minimization and safety follow-up measures have been planned in this clinical study:

CD14152.RD.06.SPR.203890 Protocol V02 - 12Dec 3.0

- a. The protocol will exclude subjects who experienced an adverse event (AE) in the prior lead-in study that, in the opinion of the Investigator, could indicate continued treatment with nemolizumab would present an unreasonable risk for the subject.

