ACT = Asthma Control Test; ADA = anti-drug antibody; AE = adverse event; DLQI = Dermatology Life Quality Index; ECG = electrocardiogram; ET = early termination; FSH = follicle-stimulating hormone; FU = follow-up; HIV = human immunodeficiency virus; ICF = informed consent form; IGA = Investigator Global Assessment; LTE = long-term extension; PEF = peak expiratory flow; POE = proof of exposure; PP NRS= peak pruritus numeric rating scale; SD NRS= sleep disturbance numeric rating scale; TB = tuberculosis; UPT = urine pregnancy test; V = visit; W = week.

- After signing the ICF, all subjects will be evaluated for study participation, based on eligibility criteria. The Week 52 study assessments from the LTE lead-in study RD.06.SPR.202699 will be used as baseline assessments for the current study.
- Subjects who relapse or discontinue prematurely (before the Week 24 visit) should complete an ET visit. If the subject discontinues for reasons other than relapse before Week 24, or will not continue with nemolizumab treatment in the LTE study, a follow-up visit should also be completed, 12 weeks (±7 days) after the last study drug injection.
- Assessments to be conducted at the unscheduled visit depend on the reason for the visit. POE and ADA analyses should only be performed at unscheduled visits that are conducted for safety reasons when safety labs are collected for the management/monitoring of an AE. When a series of unscheduled visits is needed for the monitoring of the same AE, the POE and ADA collection is not required if already done at the first unscheduled visit of the series. Additional collection of samples for POE and ADA analysis should be performed per Investigator's judgment.
- PP NRS to be recorded by subjects once daily in the evening. SD NRS to be recorded by subjects once daily in the morning and if possible, within 1 hour of getting out of bed.
- Patient-reported outcome assessments and designated safety measurements (including AE and concomitant therapies/procedures assessments) should occur before Investigator assessments, laboratory sample collections, and study drug administration.
- Subjects with a history of asthma will complete the ACT testing at all visits. Subjects with a new (de novo) diagnosis of asthma will complete the ACT testing beginning from de novo diagnosis and at all subsequent scheduled visits.

This document is confidential.

Statistical Analysis Plan for Interventional Studies

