Week 21	148	141 to 147	142 to 148
Week 22	155	148 to 154	149 to 155
Week 23	162	155 to 161	156 to 162
Week 24 ^a	169	162 to 175	163 to 176
Early Termination*	UN	7 days prior until Early termination visit (excluding early termination visit date)	6 days prior until early termination visit (including early termination visit date)

^a First 7 days data available will be used for weekly average calculation.

*For subjects with early termination, if weekly average is not available based on the slotting, additional analysis window was added and will be assigned to the week based on the slotting above. i.e., if subject

This document is confidential.

early terminated day 142, and week 21 is not available, the new window defined will be used to determine the weekly average at that week.

Safety and pharmacokinetics data will not be windowed for by-visit summary. i.e., scheduled visit data will be used for analysis.

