10.2.2. Pruritus Numeric Rating Scale (NRS)

The Pruritus NRS is a scale to be used by the subjects to report the intensity of their pruritus (itch) during the last 24 hours. Peak pruritus (PP NRS) is an assessment of the maximum itch intensity in that period.

This document is confidential.

Subjects will be asked the following question:

- CCI

The Baseline PP NRS will be the score of Week 52 visit from LTE trial.

PP NRS at all follow-up visits will be determined as an average of 7 consecutive days data up to the target study day and will be set to missing if less than 4 days data are available. Subjects will receive instructions on how to record their PP NRS scores and will complete the assessment once daily in the evening throughout the clinical study (including the run-in and the follow-up period).

PP NRS will be determined by an average as described above at every week from Baseline to Week 24 as a continuous variable.

Descriptive summary of PP NRS (OC) will be provided on the ITT and Per-Protocol Populations. Absolute change and percent change from Baseline for the PP NRS will also be included in the summary on the ITT and Per-Protocol Populations.

Absolute change from Baseline in PP NRS will be analyzed using ANCOVA based on OC, including treatment group dose regimen as factors with baseline value as covariate. The least squares means (LSMeans), standard error of LSMeans, and 95% CI for change from baseline, as well as the difference in LSMeans between the treatment groups, the two-sided 95% CI, and associated p-value will be presented. Percentage change from Baseline in PP NRS will not be analyzed because of the small sample size and potential high skewness of the data.

The analysis will be repeated:

- on Per-Protocol Population, based on OC

on ITT population, based on OC and using MMRM approach, including treatment group and dose regimen as factor, visit, interaction term between treatment and visit, and baseline value as covariate. Kenward-Roger approximation is used to estimate denominator degrees of freedom. An unstructured covariance is used to model the within-patient errors in the analysis. While applying the model, if convergence criteria not met with unstructured covariance matrix, then below mentioned covariance matrix will be applied to achieve convergence of the model. The matrix with the minimum AIC criteria will be selected for the further analysis.

- Compound Symmetry (CS)
- Ar(1) – Autoregressive (1)

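### An early but in-window Week 24 visit can leave a completer with too few diary days for a Week 24 itch score, and the SAP's fallback window does not cover completers

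*SAP*

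**What the plan says.** SAP 8.4, Table 8-2, gives each post-baseline week a 7-day diary window set by study day. Week 24 (target Day 169) is the exception: Days 162 to 175 for the evening PP NRS and Days 163 to 176 for the morning SD NRS, with the footnote "First 7 days data available will be used for weekly average calculation". The text above the table says that "the daily data collected up to Week 24 will be classified into analysis visits". A second footnote gives early-termination subjects a substitute window, the 7 days before their visit, when the slotting yields no weekly average. Subjects who complete Week 24 are not mentioned there.

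SAP 10.2.2 says that a weekly PP NRS "will be set to missing if less than 4 days data are available". The schedule in SAP 4.6 has the row "Visit Window (days) ±1 ±3 ±3 ±3 ±5 ±5 ±7"; the sixth value, ±5 days, belongs to Week 24. A footnote to that schedule has "PP NRS to be recorded by subjects once daily in the evening", so the visit-day entry comes after the visit.

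For binary endpoints, SAP 10.2 plans an observed-case analysis and an imputed analysis in which a missing relapse result counts as a relapse. For the primary endpoint, SAP 10.1.1 judges a visit on whichever of PP NRS and IGA is available.

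**The concern.** The Week 24 diary window was lengthened at its late end only. It therefore accommodates a late visit but not an early one, although the schedule permits both equally. A subject who attends early but within the window may have only a few evenings of diary inside it.

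If the score is then missing, the imputed analysis records an itch relapse for someone who finished the 24 weeks without one. This happens at the last visit of the durability period. It can affect only subjects still in the study at Week 24, because relapsers leave earlier. If nemolizumab keeps more subjects to Week 24, the miscount falls more on that arm and shrinks the difference at that visit.

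**Working it through.** **1. Reproduce the windows.** For week w the target day is 7w + 1. The evening window runs from target − 7 to target − 1, and the morning window from target − 6 to target. For w = 23 the evening window is 155–161, as printed. For w = 24 the target is 169, the evening window 162–168 and the morning window 163–169. The printed 162–175 and 163–176 are these windows with 7 days added at the late end.

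**2. Permitted Week 24 visit days.** 169 ± 5 gives Days 164 to 174, which is 11 days.

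**3. Count the pre-visit evenings.** For a visit on day v, the evenings available from Day 162 are v − 162. Suppose the diary stops at the visit. The chance of at least 4 entries is then binomial, with daily diary completion assumed at 100%, 90% or 80%.

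| Visit day | Evenings before visit | P(≥4 entries): 100% / 90% / 80% |
|---|---|---|
| 164 | 2 | 0 / 0 / 0 |
| 165 | 3 | 0 / 0 / 0 |
| 166 | 4 | 100% / 66% / 41% |
| 167 | 5 | 100% / 92% / 74% |
| 168 | 6 | 100% / 98% / 90% |
| 169 | 7 | 100% / 99.7% / 97% |

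Mornings up to and including the visit day, counted from Day 163, number the same: 2, 3, 4, 5 and 6 for Days 164 to 168. SAP 10.2.3 states no minimum for SD NRS. If the 4-day rule is meant to apply there too, SD NRS is missing for the same visits.

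**4. How often.** Visit timing is not given, so these shares are assumptions. If visits spread evenly over the 11 days, Days 164–165 hold 2/11 = 18%. If they are triangular around Day 169 (weights 1, 2, 3, 4, 5, 6, 5, 4, 3, 2, 1, sum 36), they hold 3/36 = 8%.

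**5. Size in the imputed analysis.** Assume 20 subjects per arm (40 randomized 1:1) and that every early completer's diary stops at the visit. One miscount is 1/20 = 5 points.

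- Nemolizumab, assuming 18 completers: 18 × 3/36 = 1.5 and 18 × 2/11 = 3.3 subjects, or 7.5 and 16 points.
- Placebo, assuming 10 completers: 10 × 3/36 = 0.8 and 10 × 2/11 = 1.8 subjects, or 4 and 9 points.
- Net shift in the difference: (18 − 10)/20 × 3/36 = 3.3 points and (18 − 10)/20 × 2/11 = 7.3 points. With equal numbers of completers it is zero in expectation.

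**6. Primary endpoint.** With Week 24 itch missing, the Week 24 IGA still counts, and a completer without relapse is censored at Week 24 completion. Weekly itch averages run through Week 23, which ends on Day 161. Only a relapse that shows in itch alone, and only after Day 161, could be lost.

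**The case against.** The strongest reply is that the effect is narrow. It touches one secondary binary endpoint at one of six post-baseline visits, and there only the imputed repeat; SAP 10.2.2 puts the observed-case analysis first. It is certain only for visits on Days 164 and 165. It also requires the diary to stop at the visit, which the SAP does not settle: Section 8.4 slots data up to Week 24, Section 10.2.2 averages up to the target day yet has the diary kept through follow-up, and Table 8-2 runs past the target day. For a completer who does not enter the LTE and keeps the diary going, later entries fill the score. All of this stands, and it limits the weight of the point. It does not remove the gap for a compliant early visit.

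A reader might go further and infer that the Week 24 score is contaminated by nemolizumab restarted in the LTE. The protocol says "Subjects who complete the study through Week 24 are eligible to re-enroll in the LTE study" and, of an earlier study, "The decrease in itching sensation was rapid, within the first week following the first injection". For a Day 164 visit, the first seven window days (162–168) would include five from the visit day onward. Protocol 10.3.1 requires 3 weeks between doses, so an LTE dose on Day 164 is possible if the Week 20 dose fell by Day 143 (164 − 21), but not if it fell on Days 144 to 146. Prompt dosing is therefore possible, but contamination is not shown. The follow-up period is for subjects who will not continue nemolizumab in the LTE, neither document says that LTE diary data are pooled into this study, and Section 8.4 can be read as excluding them. What remains is that the SAP states no explicit cut-off at the first LTE injection.

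A reader might also take the 7.5 to 16 points above as the bias in the treatment comparison. That is a one-arm figure. Early visits occur in both arms, so the net shift is smaller.

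**Conclusion.** The gap is real and minor. If the diary stops at the visit, a completer seen within the permitted window on Day 164 or 165 cannot have a Week 24 PP NRS score, and visits on Days 166 to 168 are at risk if entries are skipped. The imputed analysis of PP NRS increase of at least 4 points then scores a non-relapsing completer as a relapse at Week 24; the observed-case analysis loses the subject at that visit. The primary endpoint is essentially unaffected.

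The firm figures are the day counts and the 5 points per miscount on an arm of 20. The net shift of about 3 to 7 points is only an illustration. It rests on assumed completers (18 and 10), assumed visit timing and diaries that all stop at the visit. The documents do not support a finding of drug contamination.

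**What to change.** In SAP Table 8-2, extend the early-termination footnote to completers. If the Week 24 weekly average is not available from the slotting, use the 7 evenings before the actual Week 24 visit for PP NRS, and the 7 mornings up to and including it for SD NRS. Every permitted visit day then has 7 candidate diary days. As a safeguard, state that diary entries after the first LTE injection are not used for the Week 24 score. There is no need to re-anchor the score for completers whose average is available from the slotting.

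The cost is two sentences and a small programming change before unblinding, with no new data. The drawback is overlap with Week 23: a Day 164 visit would use evenings 157 to 163, of which five (157–161) also feed the Week 23 average. The overlap falls to 4, 3, 2 and 1 days for visits on Days 165 to 168.
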